## 8. SAFETY ANALYSES

Safety data will be presented separately from each period (Parts A/B, Part C and Part D) in tabular format and summarized descriptively according to GSK's Integrated Data Standards Library (IDSL) standards.

The safety analyses will be based on the following analysis populations for each study period, unless otherwise specified:

Period	Population
Parts A/B	As Treated (AT) [Part A/B]
Part C	Intent-to-Treat (ITT) [Part C  ]
Part D	As Treated (AT) [Part D  ]

 - All analyses of Part C and Part D data will be analysed according to the treatment each subject received for more than 50% of injections within Part C (see Section 5.1).

### 8.1. Adverse Events Analyses

Adverse events analyses including the analysis of adverse events (AEs), Serious (SAEs) and other significant AEs will be based on GSK Core Data Standards.

AEs occurring during the on-treatment phase will be summarised separately for each period (Parts A/B, Part C and Part D). Adverse events will be coded using the latest version of the Medical Dictionary for Regulatory Activities (MedDRA).

The number and percentage of subjects experiencing at least one AE will be summarised. Exposure adjusted rates of AEs during Part C will also be presented to account for the length of subject exposure within the double-blind treatment period. For the definition of exposure adjusted AEs, see Section 11.6.4.

The details of the planned displays are provided in [Appendix 11](#): List of Data Displays.

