	
of treatment benefit after withdrawal of mepolizumab [Haldar, 2014], however, this has not been prospectively evaluated in subjects after long-term treatment with mepolizumab.
	
Subjects will be provided with rescue albuterol/salbutamol throughout the study.
 
Subject's condition will be assessed at clinic visits every 4 weeks.
 
Subjects' symptoms and rescue medication usage will be tracked daily via eDiary. Subjects with increasing respiratory symptoms indicative of worsening of asthma will automatically be notified through the symptom diary to contact their investigator for further evaluation. Investigators will also receive alerts, and review eDiary data weekly.
 
Additionally, to minimize the impact of significant worsening due to withdrawal of therapy over 52 weeks, subjects may optionally switch to open-label mepolizumab (Part D) per investigator discretion after experiencing one clinically significant asthma exacerbation.

Potential risk for rebound eosinophilia with associated clinical consequences
	
Early published data with Schering-Plough anti- IL5 mAb suggested potential for rebound eosinophilia and disease exacerbation when treatment was stopped [Kim, 2004; Gevaert, 2006]; however, no standard definition of rebound was used and criteria for reporting were variable.
 
There have been no verbatim reports of
	
Daily monitoring of SAEs by medical monitor; regular systematic review of AE/SAE data from ongoing studies by a GSK safety review team
 
Standard safety assessments to be conducted as outlined in protocol

Potential Risk of Clinical Significance	Summary of Data/Rationale for Risk	Mitigation Strategy
	‘rebound’ from completed clinical trials of subjects with asthma, atopic dermatitis and eosinophilic esophagitis. Furthermore, the data do not support an exaggerated return of symptoms after cessation of treatment.	
Study Procedures		
Potential risk for injury with phlebotomy	Risks with phlebotomy include bruising, bleeding, infection, nerve damage.	Procedures to be performed by trained personnel (i.e., study nurse)

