6.6. Discontinuation of Investigational Product (IP) during Part C or Part D

Subjects in study Part C or D who have permanently discontinued double-blind or open-label IP are NOT required to withdraw from the study. Subjects have the right to permanently discontinue IP before the end of the study. A subject may also be asked to discontinue IP at the investigator's discretion or because the subject met the protocol defined IP discontinuation criteria detailed below. Subjects who discontinue IP, but remain in the study will be treated per local standard of care, according to the judgment of the investigator.

Subjects in Parts C or D of the study **MUST** discontinue IP permanently if either 1, 2 or 3 of the following stopping criteria are met:

1. **Liver Chemistry:** Meets any of the protocol-defined liver chemistry stopping criteria (see [Appendix 2](#)).

Liver chemistry stopping and increased monitoring criteria have been designed to assure subject safety and evaluate liver event etiology (in alignment with the FDA premarketing clinical liver safety guidance).

<http://www.fda.gov/downloads/Drugs/GuidanceComplianceRegulatoryInformation/Guidances/UCM174090.pdf>

If the liver chemistry stopping criteria are met by any subject participating in this study, treatment restart or re-challenge is not permitted.

2. **Pregnancy:** Positive pregnancy test

3. **ECG:** Discontinuation is required if any of the following ECG criteria are met during the study:
- QTcF > 500 msec or uncorrected QT > 600 msec
 - Change from Visit B1 baseline: QTcF > 60 msec

For patients with underlying **bundle branch block**, follow the discontinuation criteria listed below:

Visit B1 Baseline QTc with Bundle Branch Block	Discontinuation QTc with Bundle Branch Block
< 450 msec	> 500 msec
450 – 480 msec	≥ 530 msec [Note: QTc(F) > 500 msec for Korean subjects]

Details on performing ECG assessments can be found in Section 8.4.5.

Subjects in Part C who meet IP discontinuation criteria 1, 2 or 3 will not be eligible to switch to open-label Part D.

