Subjects who have permanently discontinued IP and have not withdrawn consent may continue in the study. Subjects wishing to remain in the study will complete an IP Discontinuation Visit (approximately 4 weeks after the last dose and may be at the same time as a scheduled visit) and continue to attend the clinic visits at the protocol designated time intervals and complete eDiary daily and weekly entries for important efficacy and safety assessments. However, if this is not possible then the investigator will encourage the subject to participate in as much of the study as they are willing (or able) to. Guidance is provided in the study reference manual (SRM) and can be used by the investigator to discuss and agree the appropriate level of ongoing study participation with subjects, after they have discontinued IP.

If the subject is unable to visit the clinic to complete any study assessments which require physical presence of the subject, visits will occur by telephone contact to review the following:

- Exacerbations
- Adverse Event (AE)/Serious Adverse Events (SAEs)
- Concomitant medications

Subjects discontinuing IP, but remaining in the study should continue to record on their paper diary any medical problems experienced during the study, and any medication taken for those medical problems.

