8.4.1.1. Time period and Frequency for collecting AE and SAE information

- AEs will be collected from the Screening visit (Visit 1), until the Exit Visit or EW (see [Section 8.4.1.3](#)), at the timepoints specified in the Time and Events Tables ([Section 8.1](#)).
- Medical occurrences that begin prior to the start of study treatment but after obtaining informed consent may be recorded on the Medical History/Current Medical Conditions section of the CRF.
- Any SAEs assessed **as related** to study participation (e.g., protocol-mandated procedures, invasive tests, or change in existing therapy) or related to a GSK concomitant medication will be recorded from the time a subject consents to participate in the study up to and including any Exit Visit or EW.
- All SAEs will be recorded and reported to GSK within 24 hours, as indicated in [Appendix 4](#).
- Investigators are not obligated to actively seek AEs or SAEs in former study subjects. However, if the investigator learns of any SAE, including a death, at any time after a subject has been discharged from the study, and he/she considers the event reasonably related to the study treatment or study participation, the investigator must promptly notify GSK.

NOTE: The method of recording, evaluating and assessing causality of AEs and SAEs plus procedures for completing and transmitting SAE reports to GSK are provided in [Appendix 4](#)

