#### 11.4.4. Treatment Phases (Adverse Events and Cardiovascular Events)

Adverse events and cardiovascular events will be classified into treatment phases according to the time of occurrence relative to the dates of study treatment within specific study parts as shown in the table below:

Treatment Phase	Definition
Pre-treatment	Onset Date & time < First dose of open-label mepolizumab If mepolizumab treatment is never started, then all will be classified as pre-treatment.
On-treatment (Parts A/B)	Subjects who are randomized and receive double-blind treatment: First dose of open-label mepolizumab ≤ Onset Date & time < First dose of double-blind treatment Subjects who are not randomized: First dose of open-label mepolizumab ≤ Onset Date & time ≤ Last dose of open-label mepolizumab + 28 days
Post-treatment (Parts A/B)	Subjects who are not randomized: Onset Date & time > Last dose of open-label mepolizumab + 28 days
On-treatment (Part C)	Subjects who switch to study Part D: First dose of double-blind treatment ≤ Onset Date & time < First dose of open-label mepolizumab within Part D All other Part C Subjects: First dose of double-blind treatment ≤ Onset Date & time ≤ Last dose of double-blind treatment + 28 days
Post-treatment (Part C)	Subjects who do not switch to study Part D: Onset Date & time > Last dose of double-blind treatment + 28 days
On-treatment (Part D)	First dose of open-label mepolizumab within Part D ≤ Onset Date & time ≤ Last dose of open-label mepolizumab within Part D + 28 days
Post-treatment (Part D)	Onset Date & time > Last dose of open-label mepolizumab within Part D + 28 days

Time of study treatment dosing and start/stop time of event should be considered, if collected.

Where the event onset occurs on the date of study treatment and time is not available, event assumed to have occurred following dosing.

If an AE start date is missing or partial then the AE will be considered on-treatment unless there is evidence to the contrary (e.g. month/year of onset date is present and is earlier than the month/year of first dose of treatment).

Refer to [Appendix 7: Reporting Standards for Missing Data](#) for handling of missing and partial dates in adverse events and cardiovascular events.

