3.66.	ITT (Part C)	AE1	Summary of On-Treatment Serious Adverse Events by System Organ Class and Preferred Term (Part C)		SAC
3.67.	ITT (Part C)	SHELL	Summary of Exposure Adjusted On-Treatment Serious Adverse Events by System Organ Class and Preferred Term (Part C)		SAC
3.68.	ITT (Part C)	SHELL	Summary of On-Treatment Serious Adverse Events by Age Group (12-17, 18-64, $\geq 65$ years) (Part C)		SAC
3.69.	ITT (Part C)	AE1	Summary of On-Treatment Fatal Serious Adverse Events (Part C)		SAC
3.70.	ITT (Part C)	SHELL	Summary of On-Treatment Fatal Serious Adverse Events by Age Group (12-17, 18-64, $\geq 65$ years) (Part C)		SAC
3.71.	ITT (Part C)	AE1	Summary of On-Treatment Non-Fatal Serious Adverse Events by System Organ Class and Preferred Term (Part C)		SAC
3.72.	ITT (Part C)	AE1	Summary of On-Treatment Drug-Related Serious Adverse Events by System Organ Class and Preferred Term (Part C)	Table required for plain language summary	SAC
3.73.	ITT (Part C)	AE1	Summary of On-Treatment Adverse Events Leading to Permanent Discontinuation of Study Treatment or Withdrawal from Study by System Organ Class and Preferred Term (Part C)	IDSL	SAC
3.74.	ITT (Part C)	AE16	Summary of On-Treatment Serious Adverse Events by System Organ Class and Preferred Term (Number of Subjects and Occurrences) (Part C)	FDAAA, EudraCT	SAC

Safety: Tables					
No.	Population	IDSL / Example Shell	Title	Programming Notes	Deliverable [Priority]
Adverse Events of Special Interest					
3.75.	ITT (Part C)	SHELL	Summary of On-treatment Serious Adverse Events and Adverse Events of Special Interest (Incidence, Relative Risk and Risk Difference) (Part C)		SAC
3.76.	ITT (Part C)	AE1	Summary of On-Treatment Systemic Reactions Meeting Anaphylaxis Criteria (Part C)	Present by Anaphylactic Criterion 1, 2 and 3 rather than SOC as shown in AE1 Insert footnote: "Events displayed are a subset of reactions defined by the Investigator as being systemic"	SAC
3.77.	ITT (Part C)	SHELL	Summary Profile of On-Treatment Systemic Reactions Meeting Anaphylaxis Criteria (Part C)	Insert footnote: "Events displayed are a subset of reactions defined by the Investigator as being systemic"	SAC
3.78.	ITT (Part C)	AE1	Summary of On-Treatment Adverse Events Defined by the Investigator as Being Systemic (non-allergic or allergic/hypersensitivity) Reactions (Part C)		SAC
3.79.	ITT (Part C)	SHELL	Summary Profile of On-Treatment Systemic (non-allergic or allergic/hypersensitivity) Reactions (Part C)		SAC

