3.80.	ITT (Part C)	SHELL	Summary Profile of On-Treatment Systemic Allergic Reactions (Part C)		SAC
3.81.	ITT (Part C)	SHELL	Summary Profile of On-Treatment Systemic Non-Allergic Reactions (Part C)		SAC
3.82.	ITT (Part C)	AE1	Summary of On-Treatment Adverse Events Defined by the Investigator as being Local Injection Site Reactions (Part C)		SAC
3.83.	ITT (Part C)	SHELL	Summary Profile of On-Treatment Local Injection Site Reactions (Part C)		SAC
3.84.	ITT (Part C)	AE1	Summary of On-Treatment Opportunistic Infections (Part C)		SAC
3.85.	ITT (Part C)	SHELL	Summary Profile of On-Treatment Opportunistic Infections (Part C)		SAC
3.86.	ITT (Part C)	AE1	Summary of On-Treatment Malignancies (Part C)		SAC

Safety: Tables					
No.	Population	IDSL / Example Shell	Title	Programming Notes	Deliverable [Priority]
3.87.	ITT (Part C)	SHELL	Summary Profile of On-Treatment Malignancies (Part C)		SAC
3.88.	ITT (Part C)	AE1	Summary of On-Treatment Serious Cardiac, Vascular and Thromboembolic Adverse Events (Part C)		SAC
3.89.	ITT (Part C)	SHELL	Summary Profile of On-Treatment Serious Cardiac, Vascular and Thromboembolic Adverse Events (Part C)		SAC
3.90.	ITT (Part C)	AE1	Summary of On-Treatment Serious Ischemic Adverse Events (Part C)		SAC
3.91.	ITT (Part C)	SHELL	Summary Profile of On-Treatment Serious Ischemic Adverse Events (Part C)		SAC
Cardiovascular Events and Deaths (All Causes)					
3.92.	ITT (Part C)	SHELL	Summary of Cardiovascular Events and Deaths (All Causes) Reported by the Investigator (On-Treatment, Part C)		SAC
Laboratory: Chemistry					
3.93.	ITT (Part C)	LB1	Summary of Chemistry Changes from Baseline (On-Treatment, Part C)	ICH E3 Includes Baseline values.	SAC
3.94.	ITT (Part C)	LB3	Summary of Chemistry Results (Changes from Baseline Relative to the Normal Range) (On-Treatment, Part C)	ICH E3	SAC
3.95.	ITT (Part C)	LB3	Summary of Chemistry Results (Changes from Baseline Relative to the Reference Range [Potential Clinical Importance]) (On-Treatment, Part C)	ICH E3	SAC
Laboratory: Haematology					
3.96.	ITT (Part C)	LB1	Summary of Haematology Changes from Baseline (On-Treatment, Part C)	ICH E3 Includes baseline values.	SAC
3.97.	ITT (Part C)	LB3	Summary of Haematology Results (Changes from Baseline Relative to the Normal Range) (On-Treatment, Part C)	ICH E3	SAC

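### Part C safety events starting more than 28 days after the last double-blind dose have no titled by-arm summary for subjects who stop, do not switch to Part D and stay in the study

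*SAP*

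**What the plan says.** **Follow-up continues after stopping.** Protocol 6.6: "Subjects in study Part C or D who have permanently discontinued double-blind or open-label IP are NOT required to withdraw from the study". Those who remain are to "continue to attend the clinic visits at the protocol designated time intervals and complete eDiary daily and weekly entries for important efficacy and safety assessments". Protocol 8.4.1.1 sets the collection window: "AEs will be collected from the Screening visit (Visit 1), until the Exit Visit or EW".

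**Later events get their own class.** For Part C subjects who do not switch to Part D, SAP 11.4.4 defines Post-treatment (Part C) as "Onset Date & time > Last dose of double-blind treatment + 28 days". For those who do switch, events from the first Part D dose onward are On-treatment (Part D). SAP 5.1 shows Part D data in columns split by previous Part C treatment.

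**Summaries cover the on-treatment phase.** SAP 8.1: "AEs occurring during the on-treatment phase will be summarised separately for each period (Parts A/B, Part C and Part D"). In SAP 11.11.5.5 this carries into the titles, for example Table 3.69, "Summary of On-Treatment Fatal Serious Adverse Events (Part C"), and Table 3.92, "Summary of Cardiovascular Events and Deaths (All Causes) Reported by the Investigator (On-Treatment, Part C"). The relative-risk and risk-difference display (Table 3.75) and both Part C safety figures are also on-treatment. Table 3.53, the AE overview, names no phase.

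**Listings are not restricted.** Listings 15, 18, 19 and 38 (all AEs, fatal SAEs, non-fatal SAEs, all-cause deaths) cover all enrolled subjects, with treatment, study part and phase columns.

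**The concern.** The secondary objective (Protocol 3.2) is a safety comparison between continuing mepolizumab and placebo. If randomised subjects under follow-up have serious events that the by-arm SAE, death and relative-risk tables leave out, then what those tables count depends on a post-randomisation act, namely stopping injections. Stopping may differ by arm.

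The affected group is also selected. Under Protocol 6.6, subjects who stop because they met the liver chemistry, pregnancy or ECG criteria may not enter Part D. If they stay in follow-up, their later events fall in the phase with no titled table. Subjects who switch after an exacerbation have their later events tabulated.

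The SAP does not exclude off-treatment phases on principle: Table 3.11 summarises pre-treatment SAEs.

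**Working it through.** **Step 1: where each type of Part C subject's later events go**

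| Subject | Onset more than 28 days after last double-blind dose | Titled by-arm table? |
|---|---|---|
| Switches to Part D | On-treatment (Part D) once Part D dosing starts | Yes, within Tables 3.108 to 3.158, by previous arm |
| Completes Part C | Only if the Exit Visit falls late in its ±1 week window, since the Week 48 dose + 28 days is Week 52 | No, but about a week at most within that window |
| Withdraws from the study | Little time: the Early Withdrawal visit is about 4 weeks after the last dose (Protocol 6.7.2) | No, but little to tabulate |
| Stops double-blind IP, does not switch, stays in the study | Post-treatment (Part C), possibly for many weeks | No |

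Only the last row carries material follow-up.

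**Step 2: table count**

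Tables 3.53 to 3.107 number 107 − 53 + 1 = 55. All except 3.53 are on-treatment by title, which leaves 54. None is titled for post-treatment events.

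**Step 3: the plan's own disposition figure**

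Inputs from Protocol 5.3: 300 randomised, about 120 expected to meet the Part D switch criteria, 20% withdrawing before an exacerbation, about 120 completing Part C.

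- Early stoppers: 0.20 × 300 = 60.
- Completers: 300 − 120 − 60 = 120, which matches the protocol.

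The 60 are the main documented pool for the last row of Step 1. The protocol does not separate stopping injections from leaving the study, nor say when stopping occurs. Exacerbators who stop without switching would add to the pool.

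**Step 4: illustrative follow-up time**

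Assume stopping times are uniform over 52 weeks. Mean time left is 26 weeks; less the 28-day window, 26 − 4 = 22 weeks. With r the share who stay in the study:

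subject-years = 60 × r × 22/52

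- r = 0.25 (15 subjects): 6.3
- r = 0.50 (30 subjects): 12.7
- r = 0.75 (45 subjects): 19.0

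Replacing uniform timing by a fixed stop week w gives 60 × r × (52 − w − 4)/52:

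- Low end (r = 0.25, w = 36): 60 × 0.25 × 12/52 = 3.5
- High end (r = 1, w = 12): 60 × 36/52 = 41.5

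Both r and w are assumptions. Figures are for the two arms together.

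**The case against.** Four stronger readings are tempting, and the documents do not support them.

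- **That all harm beyond 28 days goes untabulated.** It does not: Part D switchers, the larger expected group, are tabulated by previous arm.
- **That a death on day 29 or later is dropped from the fatal-SAE table.** SAP 11.4.4 classifies AEs by onset. A fatal SAE that began on day 20 with death on day 40 is on-treatment. A missing or partial AE start date also defaults to on-treatment unless there is contrary evidence.
- **That the safety of withdrawal goes unexamined.** Table 3 in Protocol 5.6.1 notes early data on another anti-IL-5 antibody that "suggested potential for rebound eosinophilia and disease exacerbation when treatment was stopped", which might suggest the rebound period is missed. But withdrawal of mepolizumab is what the placebo arm receives from randomisation, and that time is on-treatment and compared by arm. In addition, Protocol 8.3.2.1 records exacerbations as AEs only when they are serious.
- **That the events are lost.** The listings show them with treatment and phase.

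The remaining case against is fair. An on-treatment focus suits the stated objective, and exposure-adjusted AE rates allow for unequal duration. Under Protocol 6.6, subjects off injections are managed under local practice, so later differences between arms are confounded. Counts will be small. Table 3.53 might hold a post-treatment row; its shell is available only on request, although SAP 8.1 suggests otherwise. SAP 11.7.1 generally puts data up to early withdrawal into tables unless otherwise specified, but SAP 8.1 and the table titles do specify otherwise.

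These points limit scope and interpretation. They do not supply a by-arm display: a listing gives no denominator, rate or comparison.

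**Conclusion.** The point holds in a narrow form. For subjects who stop double-blind IP in Part C, do not switch and remain in the study, events with onset beyond last dose + 28 days are collected and classified but have no titled by-arm summary. The SAE, fatal-SAE, cardiovascular/death and relative-risk displays omit them by rule. Whether Table 3.53 includes them cannot be settled from the documents.

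The amount of follow-up is not documented. About 6 to 19 subject-years rests on 60 early stoppers, uniform stopping times and 25% to 75% retention; other assumptions give 3.5 to 41.5. No event count can be inferred, and no effect on a safety conclusion is shown. Sample size, power, alpha and the primary analysis are untouched. This is a cheap improvement to safety reporting and does not invalidate the planned tables.

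**What to change.** Keep the on-treatment tables as the main display. Add to SAP 8.1 and 11.11.5.5:

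1. A by-arm summary of Post-treatment (Part C) SAEs, fatal SAEs, AESIs and cardiovascular events/deaths. Define the follow-up denominator as time from last double-blind dose + 28 days to study conclusion, because SAP 11.6 defines exposure time only.
2. One by-arm table of all SAEs and deaths from first double-blind dose to study conclusion, regardless of phase, with Part D events identified. State the arm definition: randomised arm, noting any subject whose arm differs under the SAP's rule of treatment received for more than 50% of injections.

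Also state in the SAP whether Table 3.53 includes post-treatment events.

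The cost is SAP wording, one denominator definition and a few tables; the events and the phase flag already exist. No visit, assessment or treatment rule changes. The downside is small counts and events that may reflect local standard-of-care therapy, so both displays should be labelled descriptive.
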